approaches to the identification of patients who may require Contact Precautions. As part of its Guidance for Control of CRE, the CDC noted that "extensive inter-facility sharing of patients across the continuum of care has the potential to facilitate widespread regional transmission of CRE." The guidelines then suggest as a supplementary practice to standard infection control practices the placement into preemptive Contact Precautions patients transferring from high-risk settings, which may include LTCFs. Data are lacking to evaluate if this is a reasonable strategy. A review in *Clinical Microbiologic Review* stated, "[u]pon admission of patients at increased risk of CRE carriage (such as residency in an LTCF . . . ), preemptive isolation while awaiting surveillance culture results can prevent early transmission events." Preemptive Contact Precautions have been suggested for certain high risk groups in extenuating circumstances for other pathogens such as MERS-CoV  with the understanding that targeting high risk populations could mitigate pathogen transmission.

Such an empiric isolation strategy, however, may have unintended consequences. Previous studies have demonstrated that patients placed into Contact Precautions may have more adverse events, depression and delirium, and potentially worse patient satisfaction and quality of care. A prospective cohort study in four acute care facilities performing active surveillance for MRSA demonstrated that Contact Precautions were associated with activities likely to reduce transmission of MDROs such as fewer visits and better hand hygiene at exit, while simultaneously exposing patients to less HCP contact, less visitor contact and other unintended outcomes. In contrast, a recent trial of universal gown and glove use in ICU settings assessed adverse event rates in these units and found patients were no more likely to experience adverse events than in control ICUs.

For study Aim III, we will investigate the impact of preemptive Contact Precautions for residents of LTCFs admitted to acute care units on the rate of hospital acquisition of MDROs and *C. difficile*. We will also examine the potential for unintended consequences (e.g. frequency of HCP contacts, patient falls) due to this isolation strategy.

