#### **RESEARCH DESIGN AND METHODS:**

**Study design:** Pre-post withdrawal quasi-experimental study using interrupted time series analysis.

**Study sites:** Six inpatient medical units within Vanderbilt University Hospital will serve as study units. These have been selected due to a higher rate of HO-MDRO/*C. difficile* incidence and/or a higher proportion of admissions comprising LCTF patients. The proposed acute care units have an average of 4,952 patient days per month with LTCF residents comprising 4.3-5.6% of unit admissions. This percentage is likely an underestimation because not all places of patient origin are documented and transfers between units within VUH are not included in this analysis. The HO-MDRO/*C. difficile* rate of these 6 units combined was 4.62 per 1,000 patient days for 2014.

**Study procedures:** After a 6 month baseline period, all units will be transitioned to a 6 month intervention period where all patients transferred onto the study units with LTCF origin prior to admission will be placed on preemptive Contact Precautions (Figure 5). Both patients admitted directly to a study unit as well as patients transferred from a non-study unit onto a study unit will be included under the policy. A washout period of 2 weeks will be introduced before a post-intervention withdrawal period of 6 months is implemented.

Inclusion/exclusion criteria: All patients admitted to the unit will be included in the study. There will be no exclusion criteria.

**Primary outcome - Rate of hospital-onset MDRO and** *C. difficile* **infections:** Aggregate rates of all hospital-onset (HO)-MDRO infections (Table 3), including MRSA, *C. difficile*, VRE, ESBL+ GNB, CRE, and MDR *Acinetobacter*, on participating units will be calculated. As active surveillance for these pathogens is not performed at VUH, only culture specimens obtained for clinical decision making will be included. Specimens from any site (e.g. blood, urine, wound) will be included. These events will be captured daily using the Vanderbilt Infection Prevention Electronic Resource (VIPER), an HAI surveillance platform that monitors laboratory results in real time. Events will be classified as HO if the specimen was collected >3 days after admission to VUH (i.e. on or after day 4).

Secondary outcomes:

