ESBL + GNB (extended-spectrum beta-lactamase producing gram- negative bacillus)	Any E. coli , K. pneumoniae and K. oxytoca demonstrated to have ESBL activity based on results from BD Phoenix through microdilution methodology. The BD Phoenix performs ESBL testing using cephalosporins (ceftazidime/cefotaxime/ceftriaxone) + clavulanic acid.

Table 3:	Definitions	of MDROs	Included in	Primar	y Study	y Outcome
----------	-------------	----------	-------------	--------	---------	-----------

2) Subgroup examinations of individual pathogen HO-infection rates for the overall study population and the aggregate HO-MDRO/*C. difficile* infection rate for each individual study unit

**Covariates:** Several factors may affect the impact of the intervention on the primary outcome. These will be measured and included in the analysis.

**1) Hand hygiene compliance:** Study unit compliance with hand hygiene as monitored by the Vanderbilt Hand Hygiene Program^34 will be included for analysis.

2) PPE compliance: Trained study personnel will perform audits of PPE use by HCP caring for patients placed into the preemptive intervention.

**3) Antimicrobial utilization:** Use of broad-spectrum antibiotics is currently tracked as a part of the VUMC Antibiotic Stewardship Program (Co-directed by Epicenter investigator [name]). Because antibiotic use is a factor in the acquisition of MDROs and *C. difficile*, we will include a measure of broad-spectrum antimicrobial use in the analysis (measured as days of therapy [DOT]).

**Analysis:** The rates of the primary and secondary outcomes will be compared for the following phases, defined *a priori*: 6 month baseline period, 6 month intervention period, and 6 month withdrawal period. In addition, a more robust interrupted time-series regression analysis with Newey-West standard errors will be performed using bimonthly outcome rates (which will provide 12 separate time point measurements for each period).

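### Aim III lists PPE compliance as an analysis covariate, but its only stated source is audits around preemptively isolated patients, so it has no values in baseline or withdrawal

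*Protocol*

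**What the plan says.** All references are to the protocol, Specific Aim III.

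- **Covariates.** Three factors are named: hand hygiene compliance, PPE compliance and antimicrobial utilization. Of all three the protocol says: "These will be measured and included in the analysis".
- **PPE compliance.** The source is "Trained study personnel will perform audits of PPE use by HCP caring for patients placed into the preemptive intervention". No other PPE audit is described for Aim III.
- **Hand hygiene.** The source is "Study unit compliance with hand hygiene as monitored by the Vanderbilt Hand Hygiene Program", a standing programme that is not limited to isolated patients. Antimicrobial days of therapy likewise come from routine stewardship tracking.
- **Study procedures.** "After a 6 month baseline period, all units will be transitioned to a 6 month intervention period", in which patients of long-term care origin are isolated preemptively. Then: "A washout period of 2 weeks will be introduced before a post-intervention withdrawal period of 6 months is implemented".
- **Analysis.** Rates are compared across the "6 month baseline period, 6 month intervention period, and 6 month withdrawal period". An interrupted time series with Newey-West standard errors is added, using twice-monthly rates, "which will provide 12 separate time point measurements for each period".

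**The concern.** Only the intervention period contains patients in preemptive isolation. An audit restricted to the staff caring for those patients can produce no value before the policy starts or after it is withdrawn. The covariate is structurally absent from exactly the periods with which the intervention is to be compared. The other two covariates do not share this problem.

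Its role is also unclear. PPE use around preemptively isolated patients describes how well the policy is carried out. It does not exist without the policy, so it cannot confound the comparison of policy with no policy.

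At stake is any covariate-adjusted estimate of the policy's effect on hospital-onset infections. An analyst who follows the Covariates paragraph literally would get either no estimate or a very imprecise one that answers a different question. The timing matters too: a later analysis plan can drop or recode the variable, but it cannot supply baseline audits that were never done.

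**Working it through.** **1. The plan's own figure.** Sample size considerations gives 29,710 patient-days per period, 4.6 events per 1,000, and 80% power for a difference of 1.4 per 1,000.
- Events: 29,710 × 4.6/1,000 = 136.7, matching the stated 137.
- SE of the rate difference: √[(0.0046 + 0.0032)/29,710] = 0.000512.
- Power: Φ(0.0014/0.000512 − 1.96) = Φ(0.77) = 0.78, two-sided 5% assumed, since alpha is not stated.

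The stated power is reproduced to within 2 points. It rests on an unadjusted comparison of two periods and involves no covariate.

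**2. Availability.** 3 periods × 12 points = 36. PPE compliance can exist at 12 of them, and at 0 of the 24 baseline and withdrawal points.

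**3. Complete-case fit.** Only the 12 intervention rows remain.
- Segmented time series (intercept, trend, level and slope change at intervention and at withdrawal, plus PPE; 7 columns). The intervention-level column equals the intercept, its slope column is trend minus 12, and both withdrawal columns are zero. Intercept, trend and PPE remain: rank 3 of 7.
- Phase model (intercept, intervention, withdrawal, PPE; 4 columns): rank 2 of 4.

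No baseline-intervention or intervention-withdrawal contrast can be estimated in either. Without PPE, the segmented model has full rank (6 of 6).

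**4. Zero-filled, constant compliance.** PPE is a multiple of the intervention indicator: rank 6 of 7 and 3 of 4, perfect collinearity.

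**5. Zero-filled, varying compliance.** Assumptions, not protocol figures: mean 75%, SD *s* between time points of 3, 5 or 10 points. In units of residual variance, without PPE the variance of the intervention level change is

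(1/12 + 5.5²/143) + (1/12 + 6.5²/143) = 0.295 + 0.379 = 0.674.

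Adding PPE adds about 0.75²/RSS. RSS is the residual sum of squares of PPE around its own trend in the intervention phase (10 df, median 9.34 × *s*²). The variance inflation is then about 1 + 0.75²/(9.34 × *s*² × 0.674):

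| SD of compliance | Variance inflation | SE multiplied by |
|---|---|---|
| 3 points | 100 | 10 |
| 5 points | 37 | 6 |
| 10 points | 10 | 3 |

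Simulation of the same design agrees (medians 101, 37 and 10). In the simpler phase model the inflation is larger: about 131 at 5 points and 33 at 10 points (SE × 11 and × 6). In either model the intervention coefficient then refers to isolation with 0% PPE compliance.

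**6. Centred within the intervention phase, zero elsewhere.** Variance inflation is 1.0 in the phase model and about 1.02 in the segmented model. The difficulty disappears, and the intervention coefficient refers to average observed compliance.

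**The case against.** The protocol never writes out an adjusted model. It introduces the covariates as factors that may alter the intervention's impact, which could mean effect modification or fidelity as easily as confounder adjustment. Coding and model form are commonly left to a statistical analysis plan, which is not at hand. Read as a modifier centred within the intervention phase, PPE compliance costs almost nothing in precision (step 6). Complete-case deletion and uncentred zero-filling are this review's scenarios, not the protocol's.

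Much of this stands, and it limits the size of the point. It does not remove it. The text calls the variable a covariate, places it in the analysis alongside two ordinary adjustment variables, and restricts its measurement to one phase. Nothing states the modifier reading. Aim II audits PPE on units of the same hospital, but the protocol does not link those units or periods to Aim III, so those data cannot be assumed to fill the gap.

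Two stronger readings are tempting, and the document does not support them.

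- **That the effect of the policy cannot be estimated at all.** The phase comparison is listed first and carries the stated power. It needs no covariate. A time series adjusted only for hand hygiene and antimicrobial use is also estimable.
- **That adjusting for hand hygiene would remove part of the effect.** The Aim III background does cite a cohort in which Contact Precautions went with "better hand hygiene at exit". But the covariate is unit-wide compliance, documented long-term care residents are 4.3–5.6% of admissions (which the protocol thinks an underestimate), and Aim II reports programme-wide compliance already at 96%. Any shift caused by the policy is unquantified and may well be small. In an uncontrolled before-after design, hand hygiene is also a plausible time-varying confounder. No change to it is asked for.

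**Conclusion.** The point holds in a limited form. As the protocol stands, PPE compliance is to enter the Aim III analysis but has a stated source in one of three phases only. As an ordinary covariate it makes the phase contrasts inestimable with complete cases. With zero-filling it inflates the standard error of the intervention level change about 10- to 3-fold in a segmented time series. The first result follows from the design alone. The second rests on the assumed 75% mean and SDs of 3 to 10 points, and on zero-filling itself. Whatever the coding, the variable measures delivery of the intervention.

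The main question remains answerable, so this should be fixed but does not undermine the trial. It should be settled before baseline begins, because that is when the choice of what to audit is still open.

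**What to change.** Either of these resolves it with a change of wording and no extra data:

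- take PPE compliance around preemptively isolated patients out of the adjustment set and report it descriptively as intervention fidelity; or
- state that it is used only as a modifier, centred within the intervention phase and set to zero elsewhere.

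If adjustment for PPE practice is wanted, define the covariate as compliance for all patients on Contact Precautions on the study units, audited the same way in baseline, intervention and withdrawal. It would then have values at 36 of 36 points. This requires additional audits in all three phases, planned before baseline starts.

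Hand hygiene and antimicrobial days of therapy can stay as they are.

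### Aim III compares six simultaneously switched units only with themselves, so a temporary or seasonal hospital-wide change in the intervention half-year cannot be told apart from an isolation effect

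*Protocol*

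**What the plan says.** The design of Aim III (Protocol, Specific Aim III, Research Design and Methods) is given as "Pre-post withdrawal quasi-experimental study using interrupted time series analysis". Under Study sites, "Six inpatient medical units within Vanderbilt University Hospital will serve as study units"; of these units the protocol says "These have been selected due to a higher rate of" hospital-onset multidrug-resistant organism (MDRO) or *C. difficile* events and/or a larger share of admissions from long-term care.

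The timing is common to all units: "After a 6 month baseline period, all units will be transitioned to a 6 month intervention period". Then, "A washout period of 2 weeks will be introduced before a post-intervention withdrawal period of 6 months is implemented".

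The primary outcome is calculated on the participating units. Events are captured through VIPER, described as "an HAI surveillance platform that monitors laboratory results in real time". The Analysis paragraph states that "The rates of the primary and secondary outcomes will be compared for the following phases", namely the three six-month phases. It adds an interrupted time series with Newey-West standard errors and 12 points per phase. The covariates are study-unit hand hygiene compliance, audits of protective equipment use for patients in preemptive isolation, and broad-spectrum antibiotic days of therapy.

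No comparison units appear anywhere in Aim III. The Limitations paragraph does not mention their absence; it suggests a later randomized multicentre trial if the result is positive. Study procedures does refer to non-study units, from which patients may transfer in.

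**The concern.** Every contrast in the plan is a contrast between calendar periods in the same six units. Anything else that lowers the rate in the intervention half-year enters the estimate with the same sign and timing as the policy. In the interrupted time series, a level term at the switch absorbs a coincident shock just as it absorbs a true effect.

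The withdrawal phase helps if the outside change persists, because the rate then fails to return. It does not help if the change is temporary. Phases of 6, 6 and 6 months with a two-week washout start the withdrawal phase about 12.5 months after the baseline phase began. Those two phases therefore share almost the same calendar months, and the intervention sits in the opposite half of the year. An annual cycle in the outcome, or in how often clinicians send cultures, then gives a fall followed by a rebound, which is the signature the design looks for. Eighteen months of data are too short to separate an annual cycle from the phases.

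The covariates cover part of this. Hand hygiene and antibiotic use are measured. The protective equipment audit covers only patients in preemptive isolation, so it has no baseline or withdrawal value. Season, laboratory method changes, outbreaks and changes in culturing practice have no covariate.

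At stake is the conclusion in the Innovation and Limitations paragraphs, where a fall in hospital-onset infections without added harm would support preemptive isolation as a new strategy.

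**Working it through.** **Inputs.** From Sample size considerations: 4,952 patient-days a month, 29,710 per phase, 4.6 events per 1,000 patient-days, 137 events per phase, 80% power for a difference of 1.4 per 1,000, about 42 fewer events. Assumed, because not stated: a two-sided 5% test and Poisson counts.

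**1. Reproduce the protocol's figures.**
- 4,952 × 6 = 29,712 patient-days.
- 29,710 × 4.6/1,000 = 136.7 events.
- 29,710 × 1.4/1,000 = 41.6 events, so the comparison is 137 against 95.
- Two-proportion power for 4.6 against 3.2 per 1,000: 78.2%.
- Log rate ratio: ln(137/95) = 0.366; SE = √(1/137 + 1/95) = 0.1335; power = Φ(0.366/0.1335 − 1.96) = 78%.

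The stated 80% reproduces to within about 2 points. It is the power of a two-phase comparison of the study units with themselves.

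**2. False reduction against baseline, no policy effect.** Let a shared drop *d* occur in the intervention phase only. The expected test statistic is 137*d*/√(137(2 − *d*)), and the chance of a significant reduction is Φ(statistic − 1.96).
- *d* = 0.10: 13.7/16.13 = 0.85, giving 13%.
- *d* = 0.20: 27.4/15.70 = 1.74, giving 41%.
- *d* = 0.30: 41.1/15.26 = 2.69, giving 77%.

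**3. What the withdrawal phase adds.** Simulation with Poisson counts in three phases and a Wald test on the log rate ratio. The last two columns require the intervention phase to be significantly below both baseline and withdrawal. The protocol sets no such rule.

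| Shared drop | Against baseline only | Both contrasts, drop confined to intervention | Both contrasts, drop persists into withdrawal |
|---|---|---|---|
| 10% | 13% | 5% | 1% |
| 20% | 41% | 25% | 2% |
| 30% | 77% | 64% | 2% |

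A lasting step is largely screened out by the stricter reading; a temporary or seasonal drop is not.

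**4. Precision of a controlled contrast.** Compare the change in study units with the change in control units that have *k* × 137 events per phase: variance = 1/137 + 1/95 + 2/(137*k*). The documents give no volume or rate for non-study units, so *k* is assumed.
- *k* = 1: SE 0.180, power 53%.
- *k* = 1.5 (for example three times the patient-days at half the rate): SE 0.166, power 60%.
- *k* = 3: SE 0.151, power 68%.

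**5. What a control series removes.** With assumed phase-to-phase shocks of SD 10%, the uncontrolled intervention-baseline test has a two-sided error of 20%. With *k* = 3 the controlled test has 5% if both groups of units share identical shocks, 11% if the shocks correlate at 0.75, and 17% at 0.5.

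**The case against.** The protocol declares a quasi-experimental design and already has real safeguards: a withdrawal phase, a time series with 12 points per phase, and covariates for hand hygiene and antibiotic use. A reader might infer that any hospital-wide change would be read as an isolation effect. The documents do not support that. A lasting change would not reverse at withdrawal, and changes acting through hand hygiene or antibiotic prescribing are at least partly adjusted for. The 13%, 41% and 77% figures use one contrast of the three-phase plan and apply only to a drop confined to the intervention phase.

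A reader might also infer that control units would restore a clean 5% error rate at little cost. That holds only if both groups of units move identically. The study units are medical units selected partly for high rates, so other units may differ in case mix and have lower rates, which costs more power. VIPER's coverage of non-study units, and whether it holds patient-days, are not stated. Selection by rate suggests that comparative unit rates existed, but that is an inference.

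These points stand, and they argue against making a controlled contrast the decisive test. They do not remove the narrower problem: a temporary or seasonal drop still gives a false reduction in 5%, 25% or 64% of studies under the stricter two-contrast reading. The plan does not adopt even that reading; the Limitations paragraph speaks only of an impact during the intervention.

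**Conclusion.** The point holds for temporary or seasonal hospital-wide changes that fall in the intervention half-year and are not captured by the hand hygiene or antibiotic covariates. Such changes cannot be separated from the policy effect with the planned data. The exposure is material for drops of 20% or more: a false reduction in 41% of studies against baseline alone, and 25% with both contrasts required. These figures rest on 137 expected events per phase, Poisson variation, a two-sided 5% test and assumed sizes of drop; the protocol gives no information on how much hospital-wide rates actually vary.

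It does not follow that the design is invalid, that the 80% power figure is wrong for the comparison it describes, or that a control series would remove every bias. A supporting controlled analysis is a worthwhile and inexpensive improvement if the data exist.

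**What to change.** Keep the phase comparison and the interrupted time series as the primary analyses, and state that the 80% power refers to the phase comparison. Add to the Aim III Analysis paragraph, in substance:

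- As a pre-specified supporting analysis, counts of hospital-onset MDRO and *C. difficile* events and patient-days will be obtained for comparable VUH medical or other adult inpatient units not under the policy, over the same half-month intervals, after confirming that existing systems hold them.
- The change in study units relative to the change in these units will be estimated by a controlled interrupted time series or a ratio of rate ratios.
- A reduction in the study units that is matched in the control units will not be attributed to preemptive isolation.

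The control units should be named before the data are examined.

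**Cost.** Protocol wording and, if coverage is confirmed, one further extraction; no new patients or procedures. The controlled estimate is less precise: power for 137 against 95 events is about 53%, 60% or 68% with control events 1, 1.5 or 3 times those of the study units. It removes only changes shared by both groups. Transfers between units may dilute it, and it does not fully remove regression to the mean from choosing high-rate units. These limits should be stated alongside the result.

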1) Awareness: If a unit performs below target compliance goals for two or more periods, the unit leadership will receive written/electronic communication regarding the unit's below target performance (see Sample Compliance Awareness Report, Appendix) and will be provided information about resources available to improve performance, including local peers/units who are engaged in best practices. To allow units ample opportunity to demonstrate improvement, they may receive up to two awareness intervention visits before escalation to the next level.

2) *Guided Engagement:* If performance does not improve after two awareness interventions, units will receive a guided intervention, which includes in-person sharing of performance and meaningful comparisons delivered by trained study personnel.

**Analysis:** The aggregate rates of PPE compliance will be compared between both study periods, with a null hypothesis that compliance will not significantly improve from the Baseline Monitoring Period to the Awareness and Accountability Period. The primary analysis will examine the aggregate compliance in all study units, with an additional analysis stratified by acute care facility. In addition, a more robust interrupted time-series regression analysis with Newey-West standard errors will be performed using bimonthly compliance rates.

**Limitations:** Even with a robust observation program, the number of instances of HCP PPE use observed will be only a small proportion of the total number of these opportunities. Compliance measurements from the observed events may not be representative of the total, as there may be a Hawthorne Effect on HCP compliance based on the presence of an observer. We have encountered this issue with the hand hygiene program as well. Because these interventions and programs are designed to alter HCP behavior, we have found that even with the Hawthorne Effect of direct observation, the provision of regular observation and real-time feedback when lapses are noted has led to a hardwiring to expected behavior (based on other measures of hand hygiene compliance such as patient and embedded observer reports). We

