**Sample size considerations:** Existing data were used to assess sample size adequacy. Using patient-days, the mean patient days per period will be 4,952 patient days/month for a total of 29,710/period. The rate of HO-MDROs on the units of interest is 4.6/1000 patient days for an average of 137 evaluable events per period. This study will have 80% power to detect a true difference in infection rates of 1.4/1000 patient days. That means a reduction by approximately 42 events in the intervention period. Nursing home admissions (those that will receive the intervention) are at least 4.3-5.6% on target units which is likely an underestimate given the current reporting system.

**Safety:** A data safety monitoring board (DSMB) will be created to oversee any potential adverse events that would require further assessment and intervention. At present 100% of falls, including all falls with harm, have an event review as part of the VUH quality program. The current fall rate on the four proposed units is 2.6 falls/month. The DSMB will review the event analysis of all falls on the unit on a quarterly basis with more in depth interim analysis of all falls stratified by study intervention. Due to the low rates of baseline falls, there is the potential for low case counts to cause large percentage increases, making a pre-defined threshold difficult for stopping the trial. If a sustained, significant increase in falls is seen and thought to be due to the Contact Precautions intervention, then the study will be halted.

**Limitations and future directions:** The evaluation of preemptive Contact Precautions for patients with LTCF exposure will be conducted in an academic, tertiary referral hospital with high rates of hand hygiene compliance. Preemptive isolation is a supplementary strategy and may not be generalizable to acute care hospitals with suboptimal hand hygiene compliance. If an impact on HO infections is seen during the intervention without unintended consequences, then there may be other high risk epidemiologic groups that could benefit from preemptive isolation. If this trial shows a reduction in HO-MDRO rates, this strategy may benefit from a larger-multicenter trial with randomization. This study has the potential to transform how isolation policies are implemented in acute care hospitals and could reduce the risk of pathogen transmission to other HCP and their patients.

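### Newey-West errors on 12 points per phase reject too often, and the stated 80% power belongs to the crude phase comparison, not to the interrupted time series

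*Protocol*

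**What the plan says.** Specific Aim III, Study design, describes a "Pre-post withdrawal quasi-experimental study using interrupted time series analysis". The Analysis paragraph of that aim first compares outcome rates between the baseline, intervention and withdrawal phases. It then adds that "a more robust interrupted time-series regression analysis with Newey-West standard errors will be performed using bimonthly outcome rates", and notes that this yields 12 points in each phase, so 36 in all. It gives no regression terms, lag, small-sample correction or target coefficient.

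Sample size considerations for Aim III states: "This study will have 80% power to detect a true difference in infection rates of 1.4/1000 patient days". The inputs are patient-days and events per phase. No time-series model is mentioned, and neither alpha nor sidedness is given.

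Specific Aim II, Analysis, uses the same method as an addition to its primary aggregate comparison: "a more robust interrupted time-series regression analysis with Newey-West standard errors will be performed using bimonthly compliance rates". It has two six-month periods, so 24 points if bimonthly means twice a month, as it does in Aim III.

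**The concern.** Newey-West is a large-sample correction. With a dozen points per phase and several fitted terms, the residuals understate both the variance and the autocovariances, so the standard error tends to be too small. The analysis presented as the more robust one could then declare an effect that is not there well above the nominal rate.

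A second issue is the power figure. The design is labelled an interrupted time series, so a reader may carry the 80% over to it. A segmented model that estimates separate levels and slopes spends most of its information on extrapolating trends, and its power for a level change can be far lower.

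**Working it through.** **Inputs (Aim III, Sample size considerations and Analysis).** Exposure is "4,952 patient days/month for a total of 29,710/period" (4,952 × 6 = 29,712). Baseline: "The rate of HO-MDROs on the units of interest is 4.6/1000 patient days for an average of 137 evaluable events per period". Target: 4.6 to 3.2 per 1,000, which the plan describes as "a reduction by approximately 42 events in the intervention period" (1.4 × 29.71 = 41.6). Each time point has 29,710 / 12 = 2,476 patient-days and about 4.6 × 2.476 = 11.4 events. Assumed, because not stated: two-sided 5% and independent Poisson counts, unless noted.

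**1. The plan's own figure.** For two periods, SE = √((4.6 + 3.2) / 29.71) = 0.512. Then z = 1.4 / 0.512 = 2.73, and power = Φ(2.73 − 1.96) = 78%. The stated 80% is therefore a crude two-period comparison with no trend, autocorrelation, overdispersion or third phase. With a variance inflation of 1.5, z = 2.73 / √1.5 = 2.23 and power is 61%.

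**2. Power of the level change when level and slope change at each break.** Per-point variances are 4.6 / 2.476 = 1.858 (baseline) and 3.2 / 2.476 = 1.292 (intervention). With 12 equally spaced points the sum of squares of time is 143. The level change at the first break is the intervention line at its first point minus the baseline line extrapolated one step:

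variance = 1.858 × (1/12 + 6.5²/143) + 1.292 × (1/12 + 5.5²/143) = 0.704 + 0.381 = 1.085, so SE = 1.042.

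Power for 1.4 is Φ(1.4/1.042 − 1.96) = 26.9% with a normal reference and 25.5% with t on 30 degrees of freedom. Ordinary least squares gives 24% in simulation.

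**3. Power of an on/off term.** Comparing intervention with baseline and withdrawal together, SE = √(3.2/29.71 + 4.6/59.42) = 0.430. A common linear trend does not change this, because the on/off pattern is symmetric in time. Simulating a quasi-Poisson count model with trend and on/off term (3,000 runs) gives 4.9% false positives and 85.9% power, before any seasonal adjustment.

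**4. False-positive rate of Newey-West tests at nominal 5%.** Simulation with 36 points, 20,000 runs, n/(n−k) correction and t reference:

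| Model | Lag 1 | Lag 2 | Lag 3 |
|---|---|---|---|
| Level and slope change at each break | 11.3% | 15.6% | 19.5% |
| Level changes, common trend | 8.2% | 10.7% | 12.9% |
| On/off term, common trend | 6.6% | 8.6% | 10.5% |
| Phase dummies, no trend | 7.0% | 8.9% | 10.9% |

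Repeat simulations put lag 1 of the first row at up to 11.7%. Ordinary least squares gives about 5% in this setting. In the first model the Newey-West test rejects in 37%, 44% and 49% of runs under the planned effect, but only because it is oversized; size-adjusted power is about 22%.

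**5. Autocorrelation.** In the full model, Newey-West at lags 1-3 gives 16-24% false positives at an AR(1) correlation of 0.2 (least squares 9.6%) and 20-27% at 0.4 (16.4%). In the on/off model with trend at 0.4, it gives 16.4-18.0% against 18.7%.

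**6. Aim II length.** A two-phase, 24-point level-and-slope model with the Aim III counts gives about 11%, 15% and 18-19% at lags 1-3. Compliance proportions were not simulated, so this indicates the effect of series length only.

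**The case against.** Four points can be made for the plan.

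First, the Aim III Analysis lists the phase comparison before the time series, and the power sentence is built from per-phase totals that match it. Nothing assigns the 80% to the time series. This stands: the figure is correctly derived for the crude comparison. The only counterweight is the design label.

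Second, model terms and lag may sit in an analysis plan that is not shown. This also stands. A reader might infer that the planned analysis has a 12-20% error rate and 26% power. The protocol does not support that as an unconditional statement, since an on/off model fits its wording equally well and has over 80% power. The two figures also describe different tests: about 26% belongs to a correctly sized test, whereas the oversized Newey-West test rejects in 37-49%.

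Third, ordinary least squares is not generally better. Its 5% holds only for independent errors, and in the on/off model at a correlation of 0.4 Newey-West does slightly better. Neither is near 5% there.

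Fourth, in Aim II the time series is explicitly secondary and no power is claimed, so only the standard-error point applies.

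What remains is what the protocol does fix: Newey-West errors, a regression of rates, and 12 points per phase in Aim III. Every model simulated under those choices exceeded 5%.

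**Conclusion.** The point holds in a limited form. At this series length the stated standard-error method rejects too often, by a factor of roughly 1.3 to 4 with independent counts and lags 1-3: about 12-20% with level and slope changes at each break, and about 7-13% in simpler models. Positive autocorrelation raises the rate further. Describing the analysis as more robust is therefore not supported.

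The 80% is not miscalculated, but it covers only the crude phase comparison. For an immediate drop of 1.4 per 1,000, power of a correctly sized time-series test runs from about 24-26% (level change in the full segmented model) to about 86% (on/off term with common trend), depending on a choice the protocol leaves open. These power figures assume no autocorrelation and no overdispersion; the 86% also assumes that the effect reverses fully after the two-week washout.

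**What to change.** - Replace Newey-West, in Aim III and Aim II, with a method whose false-positive rate has been checked by simulation at the planned number of points.
- Prespecify one Aim III time-series model and its target coefficient. One option is a quasi-Poisson or negative-binomial model of counts with log patient-days as offset, a common trend and an on/off intervention term, with a small-sample autocorrelation adjustment as needed. The 86% was obtained without that adjustment, so the final version needs its own size and power check.
- State that the 80% refers to the crude phase comparison, and give simulated power for the chosen model over a range of autocorrelation and overdispersion.

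The cost is protocol or analysis-plan wording and a modest simulation. The price in content is a less favourable power figure if level or slope tests are kept. The on/off term avoids most of that loss but rests on no carry-over beyond the washout, which should be stated as an assumption.
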